*This layout also applies to:
Table 14.3.2.3 Listing of Withdrawals Due to Adverse Events (Safety Set)*

ABX464-301

ddMMMyyyy

Table 14.3.3.1 Summary of Laboratory Parameters: Haematology (Safety Set)

		ABX-464 100mg (N=xx)	ABX-464 50mg (N=xx)	Placebo (N=xx)	Total (N=xx)
Haematocrit					
Baseline	N	xx	xx	xx	xx
	Mean	xx.xx	xx.xx	xx.xx	xx.xx
	SD	xx.xx	xx.xx	xx.xx	xx.xx
	SEM	xx.xx	xx.xx	xx.xx	xx.xx
	Median	xx.xx	xx.xx	xx.xx	xx.xx
	Minimum	xx.x	xx.x	xx.x	xx.x
	Maximum	xx.x	xx.x	xx.x	xx.x
Week 1	N	xx	Xx	Xx	Xx
	Mean	xx.xx	xx.xx	xx.xx	xx.xx
	Etc				
Change from baseline to Week 1	N	xx	Xx	Xx	Xx
	Mean	xx.xx	xx.xx	xx.xx	xx.xx
	Etc				
Etc					
Etc					

Source: Listing 16.2.8.1

Path\Filename

Page x/y

Programming note: start each parameter on a new page

This layout also applies to:

Table 14.3.3.2 Summary of Laboratory Parameters: Biochemistry (Safety Set)

ABX464-301

ddMMyyyy

Table 14.3.3.3 Listing of Abnormal Laboratory Values (Safety Set)

Treatment	Patient number	Visit	Laboratory Parameter	Value
xxxxxx	xxx-xxxx	Week x	xxxxxxxxxxxxxxxxxxxxxx	xx.xx
			xxxxxxxxxxxxxxxxxxxxxx	xx.xx
			Etc	
		Etc		
	Etc			
Etc				

Path\filename

Page x/y

ABX464-301

ddMMMyyyy

Table 14.3.4 Vital Signs (Safety Set)

		ABX-464 100mg (N=xx)	ABX-464 50mg (N=xx)	Placebo (N=xx)	Total (N=xx)
Systolic BP (mmHg)					
Baseline	N	xx	xx	xx	xx
	Normal	xx (xx.x %)	xx (xx.x %)	xx (xx.x %)	xx (xx.x %)
	Abnormal NCS	xx (xx.x %)	xx (xx.x %)	xx (xx.x %)	xx (xx.x %)
	Abnormal CS	xx (xx.x %)	xx (xx.x %)	xx (xx.x %)	xx (xx.x %)
	Mean	xx.xx	xx.xx	xx.xx	xx.xx
	SD	xx.xx	xx.xx	xx.xx	xx.xx
	SEM	xx.xx	xx.xx	xx.xx	xx.xx
	Median	xx.xx	xx.xx	xx.xx	xx.xx
	Minimum	xx.x	xx.x	xx.x	xx.x
	Maximum	xx.x	xx.x	xx.x	xx.x
Week 1	N	xx	xx	xx	xx
	Normal	xx (xx.x %)	xx (xx.x %)	xx (xx.x %)	xx (xx.x %)
	Etc				

Etc

Etc

The denominator for each percentage is the number of non-missing observations within the column.
NCS = Not Clinically Significant; CS = Clinically Significant

Source: Listing 16.4.9
Path\Filename

Page x/y

Programmer's Note: List of variables consists of body temperature, weight, systolic and diastolic blood pressure, heart rate and respiratory rate.

ABX464-301

ddMMMyyyy

Table 14.3.5 Shift Table of Physical Examination (Safety Set)

		ABX-464 100mg (N=xx)		ABX-464 50mg (N=xx)		Placebo (N=xx)		Total (N=xx)	
		normal	abnormal	normal	abnormal	normal	abnormal	normal	abnormal
Eyes									
Baseline	N	xx (xx.x %)	xx (xx.x %)	xx (xx.x %)	xx (xx.x %)	xx (xx.x %)	xx (xx.x %)	xx (xx.x %)	xx (xx.x %)
Week 1	N	xx (xx.x %)	xx (xx.x %)	xx (xx.x %)	xx (xx.x %)	xx (xx.x %)	xx (xx.x %)	xx (xx.x %)	xx (xx.x %)
Etc									
Ears									
Baseline	N	xx (xx.x %)	xx (xx.x %)	xx (xx.x %)	xx (xx.x %)	xx (xx.x %)	xx (xx.x %)	xx (xx.x %)	xx (xx.x %)
Week 1	N	xx (xx.x %)	xx (xx.x %)	xx (xx.x %)	xx (xx.x %)	xx (xx.x %)	xx (xx.x %)	xx (xx.x %)	xx (xx.x %)
Etc									
Etc									

The denominator for each percentage is the number of non-missing observations within the column.

Source: Listing 16.4.10
Path\Filename

Page x/y

Programmer's Note: List of variables consists of eyes, ears, nose, throat, lungs/thorax, heart/cardiovascular system, abdomen, skin and mucosae, nervous system, lymph nodes, musculo-skeletal system, and, if applicable, others.

ABX464-301

ddMMMyyyy

Table 14.3.6 Electrocardiogram (Safety Set)

		ABX-464 100mg (N=xx)	ABX-464 50mg (N=xx)	Placebo (N=xx)	Total (N=xx)
PR interval					
Baseline	N	xx	xx	xx	xx
	Normal	xx (xx.x %)	xx (xx.x %)	xx (xx.x %)	xx (xx.x %)
	Abnormal NCS	xx (xx.x %)	xx (xx.x %)	xx (xx.x %)	xx (xx.x %)
	Abnormal CS	xx (xx.x %)	xx (xx.x %)	xx (xx.x %)	xx (xx.x %)
	Mean	xx.xx	xx.xx	xx.xx	xx.xx
	SD	xx.xx	xx.xx	xx.xx	xx.xx
	Median	xx.xx	xx.xx	xx.xx	xx.xx
	Minimum	xx.x	xx.x	xx.x	xx.x
	Maximum	xx.x	xx.x	xx.x	xx.x
Week 1	N	xx	xx	xx	xx
	Normal	xx (xx.x %)	xx (xx.x %)	xx (xx.x %)	xx (xx.x %)
	Etc				
Etc					
Etc					

The denominator for each percentage is the number of non-missing observations within the column.
NCS = Not Clinically Significant; CS = Clinically Significant

Source: Listing 16.4.11
Path\Filename

Page x/y

Programmer's Note: The absolute values of PR, QRS, QT and QTc will be summarised at each visit.

ABX464-301

ddMMMyyyy

Table 14.3.7 Study Drug Exposure and Compliance (Full Analysis Set)

		ABX-464 100mg (N=xx)	ABX-464 50mg (N=xx)	Placebo (N=xx)	Total (N=xx)
Number of dose intakes	N	xx	xx	xx	xx
	Mean	xx.xx	xx.xx	xx.xx	xx.xx
	SD	xx.xx	xx.xx	xx.xx	xx.xx
	Median	xx.xx	xx.xx	xx.xx	xx.xx
	Minimum	xx.x	xx.x	xx.x	xx.x
	Maximum	xx.x	xx.x	xx.x	xx.x
Study drug exposure (days)	N	xx	xx	xx	xx
	Mean	xx.xx	xx.xx	xx.xx	xx.xx
	Etc				
Compliance	N	xx (xx.x%)	xx (xx.x%)	xx (xx.x%)	xx (xx.x%)
	Yes	xx (xx.x%)	xx (xx.x%)	xx (xx.x%)	xx (xx.x%)
	No	xx (xx.x%)	xx (xx.x%)	xx (xx.x%)	xx (xx.x%)

Study drug exposure (days) is calculated as (date of last dose) - (date of first dose) + 1.

Source: Listing 16.2.5
Path\Filename

Page x/y

ABX464-301

ddMMMyyyy

Table 14.3.8 Prior Medications (Full Analysis Set)

	ABX-464 100mg (N=xx)	ABX-464 50mg (N=xx)	Placebo (N=xx)	Total (N=xx)
Any prior medication ¹	xx (xx.x%)	xx (xx.x%)	xx (xx.x%)	xx (xx.x%)
X, xxxxxxxxxxxxxxxx	xx (xx.x%)	xx (xx.x%)	xx (xx.x%)	xx (xx.x%)
X0N, xxxxxxxxxxxxxxxx	xx (xx.x%)	xx (xx.x%)	xx (xx.x%)	xx (xx.x%)
X0NXX, xxxxxxxxxxxxxxxx	xx (xx.x%)	xx (xx.x%)	xx (xx.x%)	xx (xx.x%)
xxxxxxxxxxxxxxxxxx	xx (xx.x%)	xx (xx.x%)	xx (xx.x%)	xx (xx.x%)
Etc	xx (xx.x%)	xx (xx.x%)	xx (xx.x%)	xx (xx.x%)
X0NXX, xxxxxxxxxxxxxxxx	xx (xx.x%)	xx (xx.x%)	xx (xx.x%)	xx (xx.x%)
xxxxxxxxxxxxxxxxxx	xx (xx.x%)	xx (xx.x%)	xx (xx.x%)	xx (xx.x%)
Etc	xx (xx.x%)	xx (xx.x%)	xx (xx.x%)	xx (xx.x%)
X0N, xxxxxxxxxxxxxxxx	xx (xx.x%)	xx (xx.x%)	xx (xx.x%)	xx (xx.x%)
X0NXX, xxxxxxxxxxxxxxxx	xx (xx.x%)	xx (xx.x%)	xx (xx.x%)	xx (xx.x%)
xxxxxxxxxxxxxxxxxx	xx (xx.x%)	xx (xx.x%)	xx (xx.x%)	xx (xx.x%)
Etc	xx (xx.x%)	xx (xx.x%)	xx (xx.x%)	xx (xx.x%)
Etc				
Etc				

¹ Medication that stopped prior to date of first dose.

WHO-DDE version <XX.X>

The denominator for each percentage is the number of patients in the full analysis set within the column.

Source: Listing 16.4.12.1

Path\Filename

Page x/y

*This layout also applies to:
Table 14.3.9.1 Concomitant Medications (Full Analysis Set)*

ABX464-301

ddMMMyyyy

Table 14.3.9.2 Change in Concomitant Medications (Full Analysis Set)

	ABX-464 100mg (N=xx)	ABX-464 50mg (N=xx)	Placebo (N=xx)	Total (N=xx)
Any concomitant medication	xx (xx.x%)	xx (xx.x%)	xx (xx.x%)	xx (xx.x%)
X, xxxxxxxxxxxxxxxx	xx (xx.x%)	xx (xx.x%)	xx (xx.x%)	xx (xx.x%)
X0N, xxxxxxxxxxxxxxxx	xx (xx.x%)	xx (xx.x%)	xx (xx.x%)	xx (xx.x%)
X0NXX, xxxxxxxxxxxxxxxx	xx (xx.x%)	xx (xx.x%)	xx (xx.x%)	xx (xx.x%)
xxxxxxxxxxxxxxxx	xx (xx.x%)	xx (xx.x%)	xx (xx.x%)	xx (xx.x%)
Etc	xx (xx.x%)	xx (xx.x%)	xx (xx.x%)	xx (xx.x%)
X0NXX, xxxxxxxxxxxxxxxx	xx (xx.x%)	xx (xx.x%)	xx (xx.x%)	xx (xx.x%)
xxxxxxxxxxxxxxxx	xx (xx.x%)	xx (xx.x%)	xx (xx.x%)	xx (xx.x%)
Etc	xx (xx.x%)	xx (xx.x%)	xx (xx.x%)	xx (xx.x%)
X0N, xxxxxxxxxxxxxxxx	xx (xx.x%)	xx (xx.x%)	xx (xx.x%)	xx (xx.x%)
X0NXX, xxxxxxxxxxxxxxxx	xx (xx.x%)	xx (xx.x%)	xx (xx.x%)	xx (xx.x%)
xxxxxxxxxxxxxxxx	xx (xx.x%)	xx (xx.x%)	xx (xx.x%)	xx (xx.x%)
Etc	xx (xx.x%)	xx (xx.x%)	xx (xx.x%)	xx (xx.x%)

Etc

Etc

WHO-DDE version <XX.X>

The denominator for each percentage is the number of patients in the full analysis set within the column.

Source: Listing 16.4.12.3

Path\Filename

ABX464-301

ddMMMyyyy

Listing 16.2.1.1 Patient Disposition

Treatment	Centre/ Patient number	First dose date	Last dose date	Completed study	Date of completion/ withdrawal	If not completed specify	Did subject complete the follow-up visit?	Death Date
xxxxxx	xxx- xxxx	ddMMMyyyy	ddMMMyyyy	Yes/No	ddMMMyyyy	specify	Yes/No (specify reason)	ddMMMyyyy
	xxx- xxxx	ddMMMyyyy	ddMMMyyyy	Yes/No	ddMMMyyyy	specify	Yes/No (specify reason)	ddMMMyyyy
	xxx- xxxx	ddMMMyyyy	ddMMMyyyy	Yes/No	ddMMMyyyy	specify	Yes/No (specify reason)	
	xxx- xxxx	ddMMMyyyy	ddMMMyyyy	Yes/No	ddMMMyyyy	specify	Yes/No (specify reason)	
	Etc							

Path\Filename

ABX464-301

ddMMyyyy

Listing 16.2.1.2 Discontinued Patients

Treatment	Centre/ Patient number	First dose date	Last dose date	Date of withdrawal	Main reason for withdrawal
xxxxxx	xxx-xxxx	ddMMyyyy	ddMMyyyy	ddMMyyyy	xxxxxxxxxxxxxxxxxxxxxxxxxxxx
	xxx-xxxx	ddMMyyyy	ddMMyyyy	ddMMyyyy	xxxxxxxxxxxxxxxxxxxxxxxxxxxx
	xxx-xxxx	ddMMyyyy	ddMMyyyy	ddMMyyyy	xxxxxxxxxxxxxxxxxxxxxxxxxxxx
	xxx-xxxx	ddMMyyyy	ddMMyyyy	ddMMyyyy	xxxxxxxxxxxxxxxxxxxxxxxxxxxx

Etc

Path\Filename

ABX464-301

ddMMMyyyy

Listing 16.2.3 Analysis Datasets

Treatment	Centre/ Patient number	Full Analysis Set	Per Protocol Set	Safety Set	Efficacy Set 1	Efficacy Set 2
xxxxxx	xxx-xxxx	Yes/No	Yes/No	Yes/No	Yes/No	Yes/No
	xxx-xxxx	Yes/No	Yes/No	Yes/No	Yes/No	Yes/No
	xxx-xxxx	Yes/No	Yes/No	Yes/No	Yes/No	Yes/No
	xxx-xxxx	Yes/No	Yes/No	Yes/No	Yes/No	Yes/No

Etc

Path\Filename

Page x/y

ABX464-301

ddMMMyyyy

Listing 16.2.4 Demographic Data

Treatment	Centre/ Patient number	Date of screening	Date of birth	Age (years)	Gender	Race	Weight (kg)	Height (cm)	BMI (kg/m ²)
xxxxxx	xxx-xxxx	ddMMMyyyy	ddMMMyyyy	xx	xxxx	xxxx	xx.x	xxx.x	xx.x
	xxx-xxxx	ddMMMyyyy	ddMMMyyyy	xx	xxxx	xxxx	xx.x	xxx.x	xx.x
	xxx-xxxx	ddMMMyyyy	ddMMMyyyy	xx	xxxx	xxxx	xx.x	xxx.x	xx.x
	xxx-xxxx	ddMMMyyyy	ddMMMyyyy	xx	xxxx	xxxx	xx.x	xxx.x	xx.x
	xxx-xxxx	ddMMMyyyy	ddMMMyyyy	xx	xxxx	xxxx	xx.x	xxx.x	xx.x

Etc

Path\Filename

ABX464-301

ddMMMyyyy

Listing 16.2.5 Study Drug Exposure and Compliance

Treatment	Centre/ Patient number	Date of compliance check	Date of first dose	Date of last dose	Duration of exposure (days)	Capsules used	Capsules expected to be used	Capsules returned	Capsules lost
xxxxxx	xxx-xxxx	ddMMMyyyy	ddMMMyyyy	ddMMMyyyy	xx	xx	xx	xx	xx
	xxx-xxxx	ddMMMyyyy	ddMMMyyyy	ddMMMyyyy	xx	xx	xx	xx	xx
	xxx-xxxx	ddMMMyyyy	ddMMMyyyy	ddMMMyyyy	xx	xx	xx	xx	xx
	xxx-xxxx	ddMMMyyyy	ddMMMyyyy	ddMMMyyyy	xx	xx	xx	xx	xx
	xxx-xxxx	ddMMMyyyy	ddMMMyyyy	ddMMMyyyy	xx	xx	xx	xx	xx
	xxx-xxxx	ddMMMyyyy	ddMMMyyyy	ddMMMyyyy	xx	xx	xx	xx	xx
	xxx-xxxx	ddMMMyyyy	ddMMMyyyy	ddMMMyyyy	xx	xx	xx	xx	xx
	Etc								

Etc

*Outside the visit window

Path\Filename

Page x/y

ABX464-301

ddMMyyyy

Listing 16.2.6 Efficacy Response Data: ACR20/50/70 Response

Treatment	Centre/ Patient number	ACR20 Response	ACR50 Response	ACR70 Response
xxxxxx	xxx-xxxx	Yes/No	Yes/No	Yes/No
	xxx-xxxx	Yes/No	Yes/No	Yes/No
	xxx-xxxx	Yes/No	Yes/No	Yes/No
	xxx-xxxx	Yes/No	Yes/No	Yes/No
Etc				

Path\Filename

Page x/y

ABX464-301

ddMMMyyyy

Listing 16.2.7 Adverse Event Listing

Treatment	Centre/ Patient number	Baseline date	Adverse Event SOC PT	Onset date	Resolution date /ongoing	Outcome	Serious	Severity	Relationship to study drug	Action taken with study drug	Other action taken
xxxxxxx	xxx- xxx	ddMMMyyyy	xxxxxxx xxxxxxx xxxxxxx	ddMMMyyyy	ddMMMyyyy/ Ongoing	Resolved/resolved without sequelae /Etc	Yes /No	Grade 1/ Grade 2/ etc	Yes/No	None /Temporary discontinuation /Etc	Concomitant medication (CM no.)/ Procedure (PR No.)
		ddMMMyyyy	xxxxxxx xxxxxxx xxxxxxx Etc	ddMMMyyyy	ddMMMyyyy/ Ongoing	Resolved/resolved without sequelae /Etc	Yes /No	Grade 1/ Grade 2/ etc	Yes/No	None /Temporary discontinuation /Etc	Concomitant medication (CM no.)/ Procedure (PR No.)
Etc											

Path\Filename

ABX464-301

ddMMMyyyy

Listing 16.2.8.1 Laboratory Measurements: Haematology

Parameter	Treatment	Centre/ Patient number	Visit	Was sample taken?	Result	Unit	Investigator's interpretation
Haemoglobin	xxxxxxx	xxx-xxxx	Screening	Yes/ No (reason)	xxx.xx	xxxx	Normal/ Abnormal CS/ Abnormal NCS
			Baseline	Yes/ No (reason)	xxx.xx	xxxx	Normal/ Abnormal CS/ Abnormal NCS
			Week 1*	Yes/ No (reason)	xxx.xx	xxxx	Normal/ Abnormal CS/ Abnormal NCS
			Etc		xxx.xx	xxxx	Normal/ Abnormal CS/ Abnormal NCS
		xxx-xxxx	Screening		xxx.xx	xxxx	Normal/ Abnormal CS/ Abnormal NCS
			Etc				
	Etc						
Etc							

*Outside the visit window
CS=Clinically Significant; NCS=Non Clinically Significant

Path\Filename

This layout also applies to:

Listing 16.2.8.2 Laboratory Measurements: Biochemistry

ABX464-301

ddMMMyyyy

Listing 16.4.1 Final Status

Treatment	Centre/ Patient number	First dose date	Last dose date	Completed treatment	Primary reason for discontinuation (specify)	Was the randomisation code broken? (date and reason)	Will subject enter follow- up?
xxxxxx	xxx-xxxx	ddMMMyyyy	ddMMMyyyy	Yes/No	xxxxxxxxxx (specify)	Yes (ddMMMyyy; xxxxxx)/ No	Yes/No
	xxx-xxxx	ddMMMyyyy	ddMMMyyyy	Yes/No	xxxxxxxxxx (specify)	Yes (ddMMMyyy; xxxxxx)/ No	Yes/No
	xxx-xxxx	ddMMMyyyy	ddMMMyyyy	Yes/No	xxxxxxxxxx (specify)	Yes (ddMMMyyy; xxxxxx)/ No	Yes/No
	xxx-xxxx	ddMMMyyyy	ddMMMyyyy	Yes/No	xxxxxxxxxx (specify)	Yes (ddMMMyyy; xxxxxx)/ No	Yes/No

Etc

Path\Filename

Page x/y

ABX464-301

ddMMyyyy

Listing 16.4.2 Patient Visit Dates

Treatment	Centre/ Patient number	Visit	Date
xxxxxx	xxx-xxxx	xx	ddMMyyyy
		xx	ddMMyyyy
		xx*	ddMMyyyy
		xx	ddMMyyyy
Etc			

*Outside the visit window

Path\Filename

ABX464-301

Listing 16.4.3.1 Inclusion Criteria

ddMMMyyyy

Protocol version: XXXX

Definition of criterion

1	XXXXXXXXXXXXXXXXXXXX
2	XXXXXXXXXXXXXXXXXXXX
3	Etc
4	
5	
6	
7	
8	
Etc	

Path\Filename

Page x/y

Programmer's Note: The list of criteria will be presented on the first page of the listing. Patient data will start on page 2. Repeat for each protocol amendment if the criteria change.

ABX464-301

ddMMMyyyy

Listing 16.4.3.1 Inclusion Criteria

Treatment	Centre/ Patient number	Protocol version	Criteria									
			1	2	3	4	5	6	7	8	Etc	
xxxxxx	xxx- xxxx	x.xx	Yes/No	Yes/No	Yes/No	Yes/No	Yes/No	Yes/No	Yes/No	Yes/No	Yes/No	Yes/No
	xxx- xxxx	x.xx	Yes/No	Yes/No	Yes/No	Yes/No	Yes/No	Yes/No	Yes/No	Yes/No	Yes/No	Yes/No
	xxx- xxxx	x.xx	Yes/No	Yes/No	Yes/No	Yes/No	Yes/No	Yes/No	Yes/No	Yes/No	Yes/No	Yes/No
	xxx- xxxx	x.xx	Yes/No	Yes/No	Yes/No	Yes/No	Yes/No	Yes/No	Yes/No	Yes/No	Yes/No	Yes/No
Etc												

Path\Filename

Page x/y

This layout also applies to:

Listing 16.4.3.2 Exclusion Criteria

ABX464-301

ddMMMyyyy

Listing 16.4.4 Medical History

Treatment	Centre/ Patient number	Date of UC Diagnosis	Any other conditions?	Condition SOC PT	Date of diagnosis	Ongoing/ End date
xxxxxx	xxx-xxxx	ddMMMyyyy	Yes/No	xxxxxxxxxxxxx xxxxxxxxxxxxx xxxxxxxxxxxxx	ddMMMyyyy	Yes/ No (ddMMMyyyy)
		ddMMMyyyy	Yes/No	xxxxxxxxxxxxx xxxxxxxxxxxxx xxxxxxxxxxxxx	ddMMMyyyy	Yes/ No (ddMMMyyyy)

Etc

Path\Filename

Page x/y

ABX464-301

ddMMMyyyy

Listing 16.4.5.1 Raw Efficacy Data: Individual Components of the ACR20 Response

Treatment	Centre/ Patient number	Visit	C-Reactive Protein (CRP) (mg/L)	Tender/ painful joint count (TJC) (28 joints)	Swollen joint count (SJC) (28 joints)	Patient assessment of joint pain (Pain- VAS)	Patient global assessment of disease (PtGA)	Physician's Global Assessment of Disease (PrGA)	HAQ-DI
xxxxxx	xxx-xxxx	Baseline Etc*	xx.x	xx.x	xx.x	xx.x	xx.x	xx.x	xx.x
Etc									

*Outside the visit window

Path\Filename

ABX464-301

ddMMMyyyy

Listing 16.4.5.2 Raw Efficacy Data: ESR, DAS28-CRP, DAS28-ESR, SDAI Score, CDAI Score and FACIT-Fatigue Score

Treatment	Centre/ Patient number	Visit	ESR	DAS28-CRP	DAS28-ESR	SDAI Score	CDAI Score	FACIT-Fatigue Score
xxxxxx	xxx-xxxx	Baseline Etc*	xx.x	xx.x	xx.x	xx.x	xx.x	xx.x
Etc								

*Outside the visit window

Path\Filename

ABX464-301

ddMMMyyyy

Listing 16.4.5.3 Raw Efficacy Data: Different Responses and Remissions

Treatment	Centre/ Patient number	Visit	Categorical DAS28-CRP response	LDA	DAS28-ESR remission	ACR/EULAR remission	SDAI remission	CDAI remission
xxxxxx	xxx-xxxx	Baseline Etc*	Yes/No	Yes/No	Yes/No	Yes/No	Yes/No	Yes/No
Etc								

*Outside the visit window

Path\Filename

ABX464-301

ddMMMyyyy

Listing 16.4.9 Vital Signs

Treatment	Centre/ Patient number	Visit	Date of visit	Body temperature (°C)	Weight (kg)	Systolic BP (mmHg)	Diastolic BP (mmHg)	Heart rate (beats/min)	Respiratory rate (/min)
xxxxxx	xxx-xxxx	xx	ddMMMyyyy	xx.x	xx.x	xxx	xxx	xxx	xx.x
		xx	ddMMMyyyy	xx.x	xx.x	xxx	xxx	xxx	xx.x
		xx*	ddMMMyyyy	xx.x	xx.x	xxx	xxx	xxx	xx.x
		xx	ddMMMyyyy	xx.x	xx.x	xxx	xxx	xxx	xx.x

Etc

*Outside the visit window

Path\Filename

Page x/y

ABX464-301

ddMMMyyyy

Listing 16.4.10 Physical Examination

Treatment	Centre/ Patient number	Visit	Date of Visit	Body system	Status	Abnormality
xxxxxx	xxx-xxxx	Screening	ddMMMyyyy	Eyes	Normal/ Abnormal NCS/ Abnormal CS/ Not done	xxxxxxxxxxxxxxxxxxxxxxxxxxxx
				Ear/Nose/Throat	Normal/ Abnormal NCS/ Abnormal CS/ Not done	xxxxxxxxxxxxxxxxxxxxxxxxxxxx
				Lungs/Thorax	Normal/ Abnormal NCS/ Abnormal CS/ Not done	xxxxxxxxxxxxxxxxxxxxxxxxxxxx
				Etc		
		xx*	ddMMMyyyy	Eyes	Normal/ Abnormal NCS/ Abnormal CS/ Not done	xxxxxxxxxxxxxxxxxxxxxxxxxxxx
				Etc		
				Etc		

*Outside the visit window
CS=Clinically Significant; NCS=Non Clinically Significant

Path\Filename

ABX464-301

ddMMMyyyy

Listing 16.4.11 12-Lead Electrocardiogram

Treatment	Centre/ Patient number	Visit	Date of visit	Time	PR interval (msec)	QRS width (msec)	QT interval (msec)	QTc interval (msec)	Investigator's interpretation	Abnormality
xxxxxx	xxx- xxxx	Baseline	ddMMMyyyy	hh:mm	xx	xx	xx	xx	Normal/ Abnormal NCS/ Abnormal CS	xxxxxxxxxxxx
		Week 8	ddMMMyyyy	hh:mm	xx	xx	xx	xx	Normal/ Abnormal NCS/ Abnormal CS	xxxxxxxxxxxx
		Etc*								
		Etc								
		Etc								

*Outside the visit window

CS=Clinically Significant; NCS=Non Clinically Significant

Path\Filename

Page x/y

ABX464-301

ddMMMyyyy

Listing 16.4.12.1 Prior Medications

Treatment	Centre/ Patient number	Therapy ATC Code PT	Indication	Dose	Unit	Frequency	Route	Start date (Stop date / Ongoing)	Given for pre- existing condition (Related medical history number)	Given for adverse event? (Related adverse event number)
xxxxxx	xxx-xxxx	xxxxxxxxxxxxxxxx xxxxxxxxxxxxxxxx xxxxxxxxxxxxxxxx	xxxxxxx	xx.x	xxx	xxx	xxx	ddMMMyyyy (ddMMMyyyy)	Yes (xxx) / No	Yes (xxx) / No
		xxxxxxxxxxxxxxxx xxxxxxxxxxxxxxxx xxxxxxxxxxxxxxxx	xxxxxxx	xx.x	xxx	xxx	xxx	ddMMMyyyy (ddMMMyyyy)	Yes (xxx) / No	Yes (xxx) / No
		xxxxxxxxxxxxxxxx xxxxxxxxxxxxxxxx xxxxxxxxxxxxxxxx	xxxxxxx	xx.x	xxx	xxx	xxx	ddMMMyyyy (ddMMMyyyy)	Yes (xxx) / No	Yes (xxx) / No
Etc										

Path\Filename

Page x/y

This layout also applies to:

Listing 16.4.12.2 Concomitant Medications (Programming note: can have stop date as 'ongoing')

Listing 16.4.12.3 Changes to Medications

ABX464-301

ddMMMyyyy

Listing 16.4.13 Pregnancy Test

Treatment	Centre/ Patient number	Visit	Test done	Reason not done	Date of test	Result
xxxxxx	xxx-xxxx	Screening	Yes/No/Not applicable	xxxxxxxxxxxxx	ddMMMyyyy	Positive/Negative
		xx	Yes/No/Not applicable	xxxxxxxxxxxxx	ddMMMyyyy	Positive/Negative
		xx*	Yes/No/Not applicable	xxxxxxxxxxxxx	ddMMMyyyy	Positive/Negative
		xx	Yes/No/Not applicable	xxxxxxxxxxxxx	ddMMMyyyy	Positive/Negative
		Etc				
		Etc				

*Outside the visit window

Path\Filename

ABX464-301

ddMMMyyyy

Listing 16.4.14 Laboratory Samples Collection

Parameter	Treatment	Centre/ Patient number	Visit	Sample taken	Reason not done	Date of test	Result	Interpretation
xxxxxx	xxxxxx	xxx-xxxx	Screening	Yes/No	xxxxxxxxxxxxx	ddMMMyyyy	xx	Normal/ Abnormal CS/ Abnormal NCS
			xx	Yes/No	xxxxxxxxxxxxx	ddMMMyyyy	xx	Normal/ Abnormal CS/ Abnormal NCS
			xx*	Yes/No	xxxxxxxxxxxxx	ddMMMyyyy	xx	Normal/ Abnormal CS/ Abnormal NCS
			xx	Yes/No	xxxxxxxxxxxxx	ddMMMyyyy	xx	Normal/ Abnormal CS/ Abnormal NCS
			Etc					

Etc

*Outside the visit window

CS=Clinically Significant; NCS=Non Clinically Significant

Path\Filename

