5.2.5. End of Study Visit (Week 15 / Day 105 ± 2 days)

This EOS visit applies to all premature discontinued patients and to patients not taking part to the maintenance study. Patients will perform an End of Study Visit (EOS) three weeks after last dosing. Patients will be treated according to the standard of care since the last day of study treatment.

Following examinations/procedures should be performed:

- Physical examination and vital signs;
- Body weight;
- Hematology and Biochemistry panel;
- Blood pregnancy test for all women of childbearing potential;
- Pharmacokinetics blood samples trough levels;
- 12 leads ECG (in case of premature discontinuation only);
- Record any concomitant medications;
- Adverse Events reporting.

NB#1: In case of premature discontinuation occurring during the treatment phase (D1-D84), the above examinations should be performed as an End of Study Visit.

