6. PATIENT COMPLETION AND WITHDRAWAL

6.1. Patient Completion

Treatment with ABX464/Placebo shall continue up to Week 12/ Day 83, except if a patient fulfils a premature discontinuation criterion (defined below).

On Day 84, patient will not take ABX464-301 study medication.

On Day 84, patients willing to carry on the study treatment will be able to take part in the long-term maintenance study (ABX464-302). Patient will sign the ABX464-302 specific informed consent and will start ABX464-302 study drug administration (50mg once daily).

In any other case, patients will exit the study (EOS) and will be treated according to the standard of care. The ABX464-302 follow-up study is a separate clinical protocol subject to health authorities and ethics committee approvals.

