6.3. Study Discontinuation

All patients, regardless of the completion or premature discontinuation, should perform the End of Study Visit according to the study flow-chart.

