8.2. Efficacy Analysis

Analysis of efficacy data will be carried out in the Full Analysis Set in which subjects who prematurely terminate the study will be considered failures.

The primary efficacy endpoint of the study, the ACR20 response rate, will be compared in subjects who received a given dose of ABX464 or placebo by likelihood ratio chi-square test on a 10% two-sided level.

The result of the test will be interpreted in a descriptive manner therefore no adjustment for multiple comparison is applied.

In addition, descriptive statistics will be presented by treatment arm for all secondary efficacy variables for each measurement timepoints separately for the two study groups.

These statistics include:

- Continuous variables: mean, standard deviation, minimum and maximum, stratified 95% confidence intervals, median and quartiles will be presented.
- Categorical variables: counts, rates and stratified 95% confidence intervals for the rates will be calculated.

In addition to descriptive statistics, mixed model analysis of covariance will be conducted for the following measurements:

- The change from baseline in DAS28-CRP and DAS28-ESR
- The change from baseline in the individual components of the ACR20 response (CRP, TJC(28), SJC(28), Pain-VAS, PtGA, PrGA, HAQ-DI) and in ESR
- The change from baseline in SDAI and CDAI scores
- The change from baseline in miR-124 in total blood at Week 8

In this model, treatments and stratum will be fixed effects, subjects will be random effect, and baseline values of the respective measurements will be covariates. Other explanatory variables will also be allowed to be included in the model. In order to normalize eventual skewed distributions transformation of the data will also be considered. Study groups will be compared within this model framework. All p-values will be interpreted in a descriptive manner.

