3.4 STUDY TIMEPOINTS

Eligible patients will be enrolled in study at the screening visit within 30 days prior to the first dosing / randomization (screening and baseline could occur at the same visit, if all laboratory results are available).

Patients will be treated for 12 weeks, followed by a follow-up period (21 days).

From Baseline / Day 0 onwards, randomized patients will be seen at the investigational site after 1 Week (Day 7), 2 weeks (Day 14), 4 weeks (Day 28), 8 weeks (Day 56) and 12 weeks (Day 84).

At Week 12 (Day 84 +/- 2 days), patients willing to carry on the study treatment will be able to take part in an open-label study (ABX464-302). In any other case, the subjects will exit the study (EOS) and will be treated according to the standard of care. The ABX464-302 follow-up study is a separate clinical study subject to health authorities and ethics committee approvals.

The end of study (EOS) visit will be performed three weeks after the end of treatment period.

The total duration of participation in the study will be approximately 15 to 19 weeks from screening to the last study visit (screening and baseline could occur at the same visit).

If more than one visit occurs within a window, the nearest to the scheduled time will be presented within the summaries.

See Section 16.1 for the Study Schedule.

Visits and visit windows will be as follows:

Visit		Day	Window
1	Screening	-30 to -1	
2	Baseline	0	
3	Week 1	7	± 2 days
4	Week 2	14	± 2 days
5	Week 4	28	± 2 days
6	Week 8	56	± 2 days
7	Week 12	84	± 2 days
8	Week 15	105 (Follow-up)	± 2 days

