Investigator's decision	xx (xx.x%)	xx (xx.x%)	xx (xx.x%)	xx (xx.x%)
Adverse event	xx (xx.x%)	xx (xx.x%)	xx (xx.x%)	xx (xx.x%)
Major protocol violation	xx (xx.x%)	xx (xx.x%)	xx (xx.x%)	xx (xx.x%)
Patient's decision	xx (xx.x%)	xx (xx.x%)	xx (xx.x%)	xx (xx.x%)
Withdrawal of consent	xx (xx.x%)	xx (xx.x%)	xx (xx.x%)	xx (xx.x%)
Etc	xx (xx.x%)	xx (xx.x%)	xx (xx.x%)	xx (xx.x%)

The denominator for each percentage is the number of randomized patients in the column. Completed defined as performed follow-up visit.

Source: Listing 16.2.1.1 and 16.2.1.2
Path\Filename

Page x/y

ABX464-301

ddMMMyyyy

Table 14.1.4 Demographic and Baseline Characteristics (Full Analysis Set)

		ABX-464 100mg (N=xx)	ABX-464 50mg (N=xx)	Placebo (N=xx)	Total (N=xx)
Age (years)	N	xx	xx	xx	xx
	Mean	xx.xx	xx.xx	xx.xx	xx.xx
	SD	xx.xx	xx.xx	xx.xx	xx.xx
	Median	xx.xx	xx.xx	xx.xx	xx.xx
	Minimum	xx.x	xx.x	xx.x	xx.x
	Maximum	xx.x	xx.x	xx.x	xx.x
Sex	N	xx	xx	xx	xx
	Male	xx (xx.x%)	xx (xx.x%)	xx (xx.x%)	xx (xx.x%)
	Female	xx (xx.x%)	xx (xx.x%)	xx (xx.x%)	xx (xx.x%)
Height (cm)	N	xx	xx	xx	xx
	Mean	xx.xx	xx.xx	xx.xx	xx.xx
	SD	xx.xx	xx.xx	xx.xx	xx.xx
	Median	xx.xx	xx.xx	xx.xx	xx.xx
	Minimum	xx.x	xx.x	xx.x	xx.x
	Maximum	xx.x	xx.x	xx.x	xx.x
Weight (kg)	N	xx	xx	xx	xx
	Mean	xx.xx	xx.xx	xx.xx	xx.xx
	SD	xx.xx	xx.xx	xx.xx	xx.xx
	Median	xx.xx	xx.xx	xx.xx	xx.xx
	Minimum	xx.x	xx.x	xx.x	xx.x
	Maximum	xx.x	xx.x	xx.x	xx.x
BMI (kg/m ²)	N	xx	xx	xx	xx
	Mean	xx.xx	xx.xx	xx.xx	xx.xx

	ABX-464 100mg (N=xx)	ABX-464 50mg (N=xx)	Placebo (N=xx)	Total (N=xx)
SD	xx.xx	xx.xx	xx.xx	xx.xx
Median	xx.xx	xx.xx	xx.xx	xx.xx
Minimum	xx.x	xx.x	xx.x	xx.x
Maximum	xx.x	xx.x	xx.x	xx.x

The denominator for each percentage is the number of non-missing observations within the column
 Age was calculated using DOB and date of first treatment (Visit 1) and presented as age at last birthday.
 BMI is the patient's body weight in kilograms divided by the square of the patient's height in metres.

Source: Listing 16.2.4
 Path\Filename

Page x/y

ABX464-301

ddMMMyyyy

Table 14.1.5.1 Medical History (Full Analysis Set)

	ABX-464 100mg (N=xx)	ABX-464 50mg (N=xx)	Placebo (N=xx)	Total (N=xx)
Any medical/surgical history	xx (xx.x%)	xx (xx.x%)	xx (xx.x%)	xx (xx.x%)
SOC	xx (xx.x%)	xx (xx.x%)	xx (xx.x%)	xx (xx.x%)
PT	xx (xx.x%)	xx (xx.x%)	xx (xx.x%)	xx (xx.x%)
Etc	xx (xx.x%)	xx (xx.x%)	xx (xx.x%)	xx (xx.x%)
SOC	xx (xx.x%)	xx (xx.x%)	xx (xx.x%)	xx (xx.x%)
PT	xx (xx.x%)	xx (xx.x%)	xx (xx.x%)	xx (xx.x%)
Etc	xx (xx.x%)	xx (xx.x%)	xx (xx.x%)	xx (xx.x%)
Etc				

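### The footnote to SAP Table 14.1.3 counts a patient as completed if the follow-up visit took place, so the 'Completed' row does not measure completion of the 12-week treatment period

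*SAP*

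**What the plan says.** SAP section 15, Table 14.1.3, has rows for randomised, completed and early-withdrawn patients by arm, followed by reasons for withdrawal. Its footnote states: "Completed defined as performed follow-up visit". SAP 5.1 contains no other definition of completion.

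SAP 3.4 labels Week 15/Day 105 as the follow-up visit, and the flow chart places EOS under the follow-up period, so the two names refer to the same scheduled visit.

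The documents differ on who attends it:

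- Protocol 5.2.5: "This EOS visit applies to all premature discontinued patients and to patients not taking part to the maintenance study". It adds: "In case of premature discontinuation occurring during the treatment phase (D1-D84), the above examinations should be performed as an End of Study Visit".
- SAP 3.4: patients may enter ABX464-302 at Week 12, and in any other case they exit through EOS.
- Protocol 6.3: "All patients, regardless of the completion or premature discontinuation, should perform the End of Study Visit according to the study flow-chart".

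Protocol 6.1, headed Patient Completion, runs treatment up to Week 12/Day 83 and does not mention a follow-up visit as a condition.

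**The concern.** A completion row should show how many patients in each arm got through the planned treatment period. This one counts attendance at a visit that, under Protocol 5.2.5, is meant for early stoppers and for those who decline the extension. Finishing 12 weeks and rolling over, which is the route the design offers to patients willing to continue, puts a patient outside the row. Stopping early and returning for EOS can put a patient inside it.

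The primary objective is safety, and this is the SAP's by-arm summary of completion. If rollover differs between arms, the row could show a difference in completion where none exists, or hide one. A patient could also appear under both 'Completed' and 'Early withdrawal', although the layout presents these as alternatives.

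**Working it through.** The plan states no figure to reproduce here. The check sets the rules side by side and then counts.

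**Step 1. Does a rollover patient have the visit?** Protocol 5.2.5 says "Patients will perform an End of Study Visit (EOS) three weeks after last dosing". Protocol 5.6.1 has rollover patients start ABX464-302 medication on Day 84. Their dosing continues, and a Week 15 visit in this study does not arise for them under 5.2.5 or SAP 3.4.

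**Step 2. Does an early stopper have the visit?** Yes, under both Protocol 5.2.5 and 6.3.

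**Step 3. Result by type of patient.**

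| Patient | Finished 12 weeks | 'Completed' under 5.2.5 | 'Completed' under 6.3 |
|---|---|---|---|
| Finishes, enters ABX464-302 | yes | no | yes |
| Finishes, attends EOS | yes | yes | yes |
| Stops early, attends EOS | no | yes | yes |

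Under 5.2.5 the first and third rows are wrong. Under 6.3 the third is wrong.

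**Step 4. Size.** Inputs: N = 60 randomised (Protocol 4.1), w early withdrawals, and a share r of Week 12 completers who roll over. The documents give neither w nor r, so both are assumed. All withdrawals, and all completers who do not roll over, are taken to attend EOS. Under Protocol 5.2.5:

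- true completers = 60 − w
- footnote count = (60 − w)(1 − r) + w
- patients whose status is wrong = r(60 − w) + w

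For example, with w = 6 and r = 0.5 the footnote count is 54 × 0.5 + 6 = 33, and 27 + 6 = 33 patients have the wrong status. Rollover counts are rounded to whole patients.

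| w | True completers | Footnote count at r = 0, 25, 50, 75, 100% | Wrong status at the same r |
|---|---|---|---|
| 3 | 57 | 60, 46, 32, 17, 3 | 3, 17, 31, 46, 60 |
| 6 | 54 | 60, 46, 33, 20, 6 | 6, 20, 33, 46, 60 |
| 12 | 48 | 60, 48, 36, 24, 12 | 12, 24, 36, 48, 60 |

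With w = 12 and r = 25% the footnote count equals the true count of 48, yet 24 patients have the wrong status, so a plausible total is no reassurance. Under Protocol 6.3 with full attendance the count is 60 whatever w is.

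**Step 5. Effect between arms.** Take two arms of 20 with 2 withdrawals each, so true completion is 18/20 = 90% in both. If 16 roll over in one arm and 12 in the other, the footnote gives (18 − 16) + 2 = 4/20 = 20% and (18 − 12) + 2 = 8/20 = 40%. The split is an assumption chosen to show the mechanism.

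**The case against.** The best defence is that an early stopper's EOS visit is not the follow-up visit the footnote means. SAP 3.4 ties follow-up to scheduled Day 105, SAP 10.1 labels the last visit differently for completers and early withdrawals, and a visit three weeks after an early last dose will generally fall before Day 105. If only the scheduled visit counts, and Protocol 6.3 holds for everyone, the footnote largely works. The ambiguity is real. But this defence must set aside Protocol 5.2.5 and SAP 3.4 on rollover patients, and 5.2.5 gives early stoppers the visit under the same Week 15/Day 105 heading. If only the scheduled visit counts but rollover patients skip it, the row falls to (60 − 6) × 0.5 = 27 at w = 6 and r = 50%, against 54 true completers.

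The underlying data also look recoverable. Listing 16.2.1.1 has separate columns for study completion and follow-up attendance, and Listing 16.4.1 has one for treatment completion. That stands, and it makes correction easy, but the printed definition would still be wrong.

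Two stronger inferences are tempting and not supported:

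- **That rollover patients become ACR20 failures.** Protocol 8.2 says "subjects who prematurely terminate the study will be considered failures". SAP 1.2 records a change from that rule. SAP 6.3 and 11.3 analyse efficacy on one set with Week 12 data available and one using LOCF from Week 4, with failure where there are no efficacy data. Neither set uses the completion flag. The failure sentence survives in SAP 3.5, in the sample-size text, with no link to this footnote.
- **That withdrawals are miscounted.** 'Early withdrawal' is a separate row with its own reasons, supported by Listing 16.2.1.2, and is not defined as the complement of 'Completed'. Adverse-event discontinuations have their own tables.

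**Conclusion.** The footnote is wrong as written. Under Protocol 5.2.5 and SAP 3.4 the 'Completed' row leaves out patients who finished treatment and rolled over. Early stoppers who attend EOS can enter it under 5.2.5 and under 6.3 alike. On either reading it does not measure completion as Protocol 6.1 describes it, and it can overlap with 'Early withdrawal'.

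The direction and size of the error depend on rollover and withdrawal rates that the documents do not give. Over the assumed range (3 to 12 withdrawals, rollover 0 to 100%, all withdrawals and all non-rollover completers attending EOS), between 3 and 60 of 60 patients would have the wrong completion status.

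The consequence is confined to the completion percentages by arm in one descriptive table. No test, analysis set or power figure is shown to change.

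**What to change.** - In the Table 14.1.3 footnote and in SAP 5.1, define 'Completed' as completing the treatment period through the Week 12/Day 84 visit without premature discontinuation.
- Report follow-up visit attendance as its own row, and entry into ABX464-302 as another where it is recorded.
- Reconcile Protocol 5.2.5 with 6.3 on who attends EOS, and make SAP 3.4 agree with the result.

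The cost is one definition, one footnote and one or two table rows. Study completion, treatment completion and follow-up attendance already have columns in the planned listings. No listing shell shows a field named for entry into ABX464-302, so whether that row needs extra data should be checked against the eCRF. No change to the ACR20 analysis is called for on this account.
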